10.5.4 Second Course Phase (Retreatment Period)

Participants who stop pembrolizumab and trebananib with SD or better may be eligible for up to an additional 17 cycles (approximately 1 year) of additional pembrolizumab treatment if they progress after stopping study treatment from the initial treatment phase. This retreatment is termed the Second Course Phase of this study and is only available if the study remains open and the participant meets the following conditions:

Either

- Stopped initial treatment with pembrolizumab and trebananib after attaining an investigator-determined confirmed CR according to RECIST 1.1, and
 - Was treated with at least 8 cycles of study treatment before discontinuing therapy and
 - Received at least two treatments with pembrolizumab beyond the date when the initial CR was declared

OR

- Had SD, PR or CR and stopped pembrolizumab and trebananib treatment after completion of 35 administrations (approximately 2 years) of study therapy for reasons other than disease progression or intolerability

AND

- Experienced an investigator-determined confirmed radiographic disease progression by RECIST 1.1 after stopping their initial treatment with pembrolizumab and trebananib and
- Did not receive any anti-cancer treatment since the last dose of pembrolizumab and trebananib
- Meets all of the safety parameters listed in the inclusion criteria and none of the safety parameters listed in the exclusion criteria
- The study is ongoing

Participants who restart treatment will be retreated at the same dose and dose interval as when they last received pembrolizumab. Treatment with pembrolizumab will be administered for up to one additional year.

An objective response or disease progression that occurs during the Second Course Phase for a participant will not be counted as an event for the primary analysis of either endpoint in this study.

Participants who have experienced an initial disease progression by RECIST 1.1 and have an iSD, iPR, or iCR per iRECIST after completion of 35 administrations of study intervention for reasons other than disease progression or intolerability may be considered for Second Course Phase after consultation with the Sponsor.

11. MEASUREMENT OF EFFECT

11.1 Antitumor Effect – Solid Tumors

Although the clinical benefit of these drugs has not yet been established, the intent of offering this treatment is to provide a possible therapeutic benefit, and thus the patient will be carefully monitored for tumor response and symptom relief in addition to safety and tolerability. Patients with measurable disease will be assessed by standard criteria. For the purposes of this study, patients should be re-evaluated every 12 weeks (\pm 7 days). In addition to a baseline scan, confirmatory scans will also be obtained 4-6 weeks following initial documentation of an objective response.

Response and progression will be evaluated in this study using the new international criteria proposed by the Response Evaluation Criteria in Solid Tumors (RECIST) guideline (version 1.1)

[*Eur J Ca* 45:228-247, 2009]. Changes in the largest diameter (unidimensional measurement) of the tumor lesions and the shortest diameter in the case of malignant lymph nodes are used in the RECIST criteria.

11.1.1 Definitions

Evaluable for Target Disease response. Only those participants who have measurable disease present at baseline, have received at least one cycle of therapy, and have had their disease re-evaluated will be considered evaluable for target disease response. These participants will have their response classified according to the definitions stated below. (Note: Participants who exhibit objective disease progression prior to the end of cycle 1 will also be considered evaluable.)

Evaluable Non-Target Disease Response. Participants who have lesions present at baseline that are evaluable but do not meet the definitions of measurable disease, have received at least one cycle of therapy, and have had their disease re-evaluated will be considered evaluable for non-target disease. The response assessment is based on the presence, absence, or unequivocal progression of the lesions.

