5.17 Participant Replacement Strategy

Additional participants may be enrolled to ensure that the required number of evaluable participants in each cohort is achieved. A participant that discontinues the trial for progressive disease or a drug-related AE will not be replaced and will be counted in the evaluable population of participants for the respective cohort.

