11.1.4.3 Evaluation of Best Overall Response

The best overall response is the best response recorded from the start of the treatment until disease progression/recurrence (taking as reference for progressive disease the smallest measurements recorded since the treatment started). The patient's best response assignment will depend on the achievement of both measurement and confirmation criteria.

For Participants with Measurable Disease (i.e., Target Disease)

Target Lesions	Non-Target Lesions	New Lesions	Overall Response	Best Overall Response when Confirmation is Required*
CR	CR	No	CR	> 4 wks Confirmation**
CR	Non-CR/Non-PD	No	PR	≥4 wks Confirmation**
CR	Not evaluated	No	PR	
PR	Non-CR/Non-PD/not evaluated	No	PR	
SD	Non-CR/Non-PD/not evaluated	No	SD	Documented at least once > 4 wks from baseline**
PD	Any	Yes or No	PD	no prior SD, PR or CR
Any	PD***	Yes or No	PD	
Any	Any	Yes	PD	

* See RECIST 1.1 manuscript for further details on what is evidence of a new lesion.
 
** Only for non-randomized trials with response as primary endpoint.
 
*** In exceptional circumstances, unequivocal progression in non-target lesions may be accepted as disease progression.
 
Note: Participants with a global deterioration of health status requiring discontinuation of treatment without objective evidence of disease progression at that time should be reported as “symptomatic deterioration.” Every effort should be made to document the objective progression even after discontinuation of treatment.
				

For Participants with Non-Measurable Disease (i.e., Non-Target Disease)

Non-Target Lesions	New Lesions	Overall Response
CR	No	CR
Non-CR/non-PD	No	Non-CR/non-PD*
Not all evaluated	No	not evaluated
Unequivocal PD	Yes or No	PD
Any	Yes	PD

* ‘Non-CR/non-PD’ is preferred over ‘stable disease’ for non-target disease since SD is increasingly used as an endpoint for assessment of efficacy in some trials so to assign
		

this category when no lesions can be measured is not advised
--

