14.2 Sample Size, Accrual Rate and Study Duration

Dose Escalation: The dose escalation portion of the trial will enroll between 6 and 12 patients. The minimum would occur if dose cohorts 1 and -1 stop due to excess toxicity after the first three patients in each are assessed for DLT. The maximum is based on two cohorts of 6 patients each. Patients in any dose escalation cohort who cease treatment during the DLT assessment window due to rapid progression of disease will not be counted as having a DLT, and may be replaced.

Dose Expansion: Total sample size will be 53 evaluable patients. The same criteria used to define evaluable patients for objective response in section 14.5 should be used here.

Patients with melanoma, ovarian cancer, colorectal cancer or renal cancer who receive the recommended dose in the dose escalation will be included in the dose expansion analyses.

We will close the melanoma cohort and stop enrolling on the current RCC cohort after 4 patients have been enrolled due to low accrual rate. We will continue enrolling ovarian cancer patients on the ovarian expansion cohort as planned up to 12 patients.

We performed an interim analysis of the 15 CRC patients who received the RP2D (3 in the dose escalation and 12 in the dose expansion) and observed a response rate of 7% (1 PR), 4 patients (26%) with best RECIST response of stable disease for a median of 10 months, and median OS of 9 months. The disease control rate (DCR), defined as best RECIST response of complete or partial response or stable disease of at least 6 months duration, was 33%. Since this activity exceeds the historical control in patients who were heavily pre-treated with chemotherapy (DCR 15%, median OS 5 months) (Grothey, Lancet. 2013 Jan 26;381(9863):303-12) we decided to expand the CRC cohort by adding 25 patients. We will expand the CRC cohort with a target sample size of 40 patients (15 already enrolled plus 25 additional) to assess the DCR in these patients. This will be a single-stage design that will have 85% power to detect a difference in DCR of 15% versus 30% with a one-sided $\alpha=0.1$ using a chi-squared test. The null DCR of 15% will be rejected if there are 9 or more patients with disease control out of 40 CRC patients. For analysis, we will present the DCR with a one-sided 90% exact confidence interval.

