14.5 Endpoint Definitions

Rate of DLT: The proportion of patients with DLT in each dose escalation cohort.

Objective response rate (ORR): Objective response will be determined by the best overall response designation (per RECIST 1.1) recorded between the date of first dose of trial therapy and the date of objectively documented disease progression or cessation of trial therapy, whichever occurs first. The objective response rate will be the proportion of patients achieving complete or partial response as their best response to therapy.

Progression-free survival (PFS): Time from start of trial treatment until objective disease progression (per RECIST 1.1) or death, whichever occurs first. Deaths that occur after 12 weeks following the date last known progression-free will not be counted as PFS events. For patients without progression or death within 12 weeks following the date last known progression-free, follow-up will be censored at the date of last disease assessment. Overall survival (OS): Time from start of trial treatment to death from any cause. For patients who are lost to follow-up or who have no documentation of death at the time of final analysis, follow-up will be censored at

the date of last assessment of vital status.

Time-to-progression (TTP): Time interval between the dates of the start of trial treatment and first documentation of progressive disease. In the absence of documented progressive disease, follow-up will be censored at date of last disease assessment. Deaths without prior progression will be censored events.

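### The ORR and DCR denominator is described inconsistently; if the evaluable set is used, some early failures without a re-scan can be dropped and replaced

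*Combined protocol and SAP*

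**What the plan says.** **Evaluable wording.** Section 14.2 sizes the expansion this way: "Total sample size will be 53 evaluable patients". It adds: "The same criteria used to define evaluable patients for objective response in section 14.5 should be used here". Section 14.5 contains no evaluability criteria, and it does not define DCR, which appears only in 14.2. Section 11.1.1 supplies the only definition for target-disease response: patients with measurable disease at baseline who "have received at least one cycle of therapy, and have had their disease re-evaluated will be considered evaluable for target disease response". It makes one exception: "Participants who exhibit objective disease progression prior to the end of cycle 1 will also be considered evaluable". Section 5.17 says "Additional participants may be enrolled to ensure that the required number of evaluable participants in each cohort is achieved", with this limit: "A participant that discontinues the trial for progressive disease or a drug-related AE will not be replaced and will be counted in the evaluable population".

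**All-patient wording.** Section 14.5 defines ORR as a proportion of patients, without restriction. Section 14.6 bases the secondary endpoints on patients enrolled in the expansion cohorts. In 14.2 the colorectal (CRC) rule is 9 or more with disease control out of 40 CRC patients, and the interim rates use all 15 CRC patients who received the RP2D.

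**Response window.** Section 14.5 counts responses up to the "date of objectively documented disease progression or cessation of trial therapy, whichever occurs first". Section 11.1.4.3 says "The best overall response is the best response recorded from the start of the treatment until disease progression/recurrence". Section 10.5.2 continues imaging every 12 weeks after treatment stops for a reason other than progression.

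**The concern.** Sections 14.2, 11.1.1 and 5.17 together describe an evaluable-patient analysis with replacement, while 14.5, 14.6 and the interim describe an all-patient analysis. Either can be defended from the text, so the choice could be made after the data are seen.

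The choice matters because scheduled re-evaluation is every 12 weeks (11.1). A patient who dies, deteriorates symptomatically, withdraws or stops for an unrelated adverse event without a re-scan fails the 11.1.1 definition, and 5.17 does not protect that patient from replacement. Such a patient cannot count as disease control, which needs a complete or partial response or stable disease of at least 6 months. Removal therefore can only raise the rate. The CRC DCR is the one efficacy endpoint with a formal reject rule, set against a fixed historical 15%. An interim on all treated patients followed by a final analysis on evaluable patients would also mix two sets within one 40-patient test.

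The response window is a second inconsistency, and it works in the other direction: a response first seen on an off-treatment scan counts under 11.1.4.3 and is lost under 14.5.

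**Working it through.** **Counts.** 12 ovarian + 37 CRC + 4 RCC = 53, so the evaluable total in 14.2 equals the planned enrolled total. The DCR test has 15 + 25 = 40 patients, which is 3 from escalation plus 37 from expansion. The interim DCR is 5/15 = 33.3%.

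**The plan's own power figure.** Inputs from 14.2: n = 40, null 15%, alternative 30%, one-sided alpha 0.1, chi-squared (normal approximation) test.

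- Critical count: 40 × 0.15 + 1.2816 × √(40 × 0.15 × 0.85) = 8.89, so the cut-off is 9, as stated.
- Power: Φ[(0.15 − 1.2816 × √(0.15 × 0.85/40)) / √(0.30 × 0.70/40)] = 0.858. The stated 85% reproduces.
- Exact binomial for at least 9/40: 0.135 at a true 15%, and 0.889 at 30%.

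The gap between 0.135 and the stated 0.1 comes from using a normal approximation. It is present before any denominator effect.

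**Denominator effect with replacement.** Let q be the share of treated patients who have no re-scan, are all failures, and are replaced until 40 are evaluable. The apparent DCR is 0.15/(1 − q), and the number treated is 40/(1 − q). The documents do not give q, so it is an assumption. The lower end is 0. The upper end of 19% is the share dead by week 12 under exponential survival at the interim median OS of 9 months: 12 weeks = 2.76 months, and 1 − exp(−ln 2 × 2.76/9) = 0.191. It is a generous bound, because it treats every early death as unscanned and replaceable.

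| q (assumed) | Apparent DCR | P(at least 9/40) | Treated to reach 40 |
|---|---|---|---|
| 0 | 15.0% | 0.135 | 40 |
| 5% | 15.8% | 0.170 | 42.1 |
| 10% | 16.7% | 0.213 | 44.4 |
| 19% | 18.5% | 0.316 | 49.4 |

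If the first 15 stay on the all-treated basis used at the interim, only the 25 added patients are affected. P(Bin(15, 0.15) + Bin(25, 0.15/(1 − q)) ≥ 9) is then 0.156, 0.182 and 0.241 at q = 5%, 10% and 19%.

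**One worked case.** With 4 unscanned patients replaced, 9/40 = 22.5% evaluable is 9/44 = 20.5% of those treated. With 4 dropped from 40 and not replaced, the reported rate is 9/36 = 25.0% against 9/40 = 22.5%. In that case the number with disease control among 40 treated is unchanged, so the chance of reaching 9 stays at 0.135, and only the reported rate rises.

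**Room for replacement.** Section 1.1 caps the study at 60 and CRC expansion enrolment at 37. The expansion uses 53, leaving 60 − 53 = 7, while 14.2 expects 6 to 12 in escalation. Read literally, the caps leave almost no room for the 2 to 9 extra patients in the table. Section 5.17 nevertheless permits extra enrolment, and the documents do not say which provision governs.

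**The case against.** A reader might infer that ORR and DCR are defined on the evaluable set and that early failures as a class leave the denominator. The documents do not support either statement. No section names the evaluable set as the denominator, 14.5 and 14.6 read the other way, and the only DCR reported so far used every CRC patient treated at the RP2D. Objective progression before the end of cycle 1 is kept by 11.1.1, and stops for progression or a drug-related adverse event are kept by 5.17. These may well be most of the early failures.

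The study calendar also marks a chest, abdomen and pelvic CT at the end-of-treatment visit, and 10.4.2 asks for final-visit procedures at discontinuation. Section 11.1.4.3 asks for every effort to document progression after symptomatic deterioration. Many patients who stop before week 12 should therefore have a re-scan, although the calendar's 12-week CT footnote leaves the timing of that scan somewhat unclear.

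All of this stands, and it narrows the group at risk to early deaths, refusals and other stops without a scan. It also makes any inflation a possibility of unknown size. Safety is the primary objective, and 14.6 calls the within-disease analyses primarily descriptive. What remains is that 14.2 sends the reader to criteria that do not exist, that two denominators are available for a test with a fixed cut-off, and that a drug-related stop before any scan is evaluable under 5.17 but may not be under 11.1.1.

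**Conclusion.** The denominator for ORR and DCR is inconsistent across 5.17, 11.1.1, 14.2, 14.5 and 14.6. If the evaluable set is used with replacement, the bias is upward. Its size rests on an assumed unscanned share of 0–19%, with all unscanned patients treated as failures, which takes the exact chance of passing the CRC rule at a true 15% from 0.135 to 0.32. The upper figure is unlikely to be reached, given the retained categories, the end-of-treatment CT and the enrolment caps. The response-window mismatch between 14.5 and 11.1.4.3 is a separate error that lowers ORR; it neither supports nor cancels the first. This should be fixed, chiefly because a few patients can decide the 9/40 test. Confidence is moderate.

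**What to change.** - In 14.2, 14.5 and 14.6, define the ORR and DCR denominator as all patients in the disease cohort who received at least one dose at the RP2D. Count those with no post-baseline assessment as non-responders without disease control, and do not replace them for efficacy. Keep the evaluable set as a sensitivity analysis.
- Align 5.17 and 11.1.1 with this, and remove the reference in 14.2 to criteria that 14.5 does not hold.
- In 14.5, end the response window at progression or the start of new anti-cancer therapy, whichever is first, in place of the end of trial therapy. Align 11.1.4.3 to the same window.

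This is a wording change to the protocol as well as to the statistical section, because 5.17, 11.1.1 and 11.1.4.3 are affected. No new data are needed, since 10.5.2 already collects off-treatment disease status until new therapy starts. The downside is that reported rates may be slightly lower than on the evaluable set.

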11.1.2 Disease Parameters

Measurable disease. Measurable lesions are defined as those that can be accurately measured in at least one dimension (longest diameter to be recorded) as ≥ 20 mm by chest x-ray or ≥ 10 mm with CT scan, MRI, or calipers by clinical exam. All tumor measurements must be recorded in millimeters (or decimal fractions of centimeters).

Note: Tumor lesions that are situated in a previously irradiated area might or might not be considered measurable.

Malignant lymph nodes. To be considered pathologically enlarged and measurable, a lymph node must be ≥ 15 mm in short axis when assessed by CT scan (CT scan slice thickness recommended to be no greater than 5 mm). At baseline and in follow-up, only the short axis will be measured and followed.

Non-measurable disease. All other lesions (or sites of disease), including small lesions (longest diameter < 10 mm or pathological lymph nodes with ≥ 10 to < 15 mm short axis), are considered non-measurable disease. Bone lesions, leptomeningeal disease, ascites, pleural/pericardial effusions, lymphangitis cutis/pulmonitis, inflammatory breast disease, abdominal masses (not followed by CT or MRI), and cystic lesions are all considered non-measurable.

Note: Cystic lesions that meet the criteria for radiographically defined simple cysts should not be considered as malignant lesions (neither measurable nor non-measurable) since they are, by definition, simple cysts.

‘Cystic lesions’ thought to represent cystic metastases can be considered as measurable

lesions, if they meet the definition of measurability described above. However, if non-cystic lesions are present in the same participant, these are preferred for selection as target lesions.

Target lesions. All measurable lesions up to a maximum of 2 lesions per organ and 5 lesions in total, representative of all involved organs, should be identified as **target lesions** and recorded and measured at baseline. Target lesions should be selected on the basis of their size (lesions with the longest diameter), be representative of all involved organs, but in addition should be those that lend themselves to reproducible repeated measurements. It may be the case that, on occasion, the largest lesion does not lend itself to reproducible measurement in which circumstance the next largest lesion which can be measured reproducibly should be selected. A sum of the diameters (longest for non-nodal lesions, short axis for nodal lesions) for all target lesions will be calculated and reported as the baseline sum diameters. If lymph nodes are to be included in the sum, then only the short axis is added into the sum. The baseline sum diameters will be used as reference to further characterize any objective tumor regression in the measurable dimension of the disease.

Non-target lesions. All other lesions (or sites of disease) including any measurable lesions over and above the 5 target lesions should be identified as **non-target lesions** and should also be recorded at baseline. Measurements of these lesions are not required, but the presence, absence, or in rare cases unequivocal progression of each should be noted throughout follow up.

11.1.3 Methods for Evaluation of Disease

All measurements should be taken and recorded in metric notation using a ruler, calipers, or a digital measurement tool. All baseline evaluations should be performed as closely as possible to the beginning of treatment and never more than 4 weeks before the beginning of the treatment.

The same method of assessment and the same technique should be used to characterize each identified and reported lesion at baseline and during follow-up. Imaging-based evaluation is preferred to evaluation by clinical examination unless the lesion(s) being followed cannot be imaged but are assessable by clinical exam.

Clinical lesions. Clinical lesions will only be considered measurable when they are superficial (*e.g.*, skin nodules and palpable lymph nodes) and ≥ 10 mm in diameter as assessed using calipers (*e.g.*, skin nodules). In the case of skin lesions, documentation by color photography, including a ruler to estimate the size of the lesion, is recommended.

Chest x-ray. Lesions on chest x-ray are acceptable as measurable lesions when they are clearly defined and surrounded by aerated lung; however, CT is preferable.

Conventional CT and MRI. This guideline has defined measurability of lesions on CT scan based on the assumption that CT thickness is 5mm or less. If CT scans have slice

thickness greater than 5 mm, the minimum size of a measurable lesion should be twice the slice thickness. MRI is also acceptable in certain situations (*e.g.* for body scans).

Use of MRI remains a complex issue. MRI has excellent contrast, spatial, and temporal resolution; however, there are many image acquisition variables involved in MRI, which greatly impact image quality, lesion conspicuity, and measurement. Furthermore, the availability of MRI is variable globally. As with CT, if an MRI is performed, the technical specifications of the scanning sequences used should be optimized for the evaluation of the type and site of disease. Furthermore, as with CT, the modality used at follow-up should be the same as was used at baseline and the lesions should be measured/assessed on the same pulse sequence. It is beyond the scope of the RECIST guidelines to prescribe specific MRI pulse sequence parameters for all scanners, body parts, and diseases. Ideally, the same type of scanner should be used and the image acquisition protocol should be followed as closely as possible to prior scans. Body scans should be performed with breath-hold scanning techniques, if possible.

Ultrasound. Ultrasound is not useful in assessment of lesion size and should not be used as a method of measurement. Ultrasound examinations cannot be reproduced in their entirety for independent review at a later date and, because they are operator dependent, it cannot be guaranteed that the same technique and measurements will be taken from one assessment to the next. If new lesions are identified by ultrasound in the course of the study, confirmation by CT or MRI is advised. If there is concern about radiation exposure from CT, MRI may be used instead of CT in selected instances.

Endoscopy, Laparoscopy. The utilization of these techniques for objective tumor evaluation is not advised. However, such techniques may be useful to confirm complete pathological response when biopsies are obtained or to determine relapse in trials where recurrence following complete response (CR) or surgical resection is an endpoint.

Tumor markers. Tumor markers alone cannot be used to assess response. If markers are initially above the upper normal limit, they must normalize for a participant to be considered in complete clinical response. Specific guidelines for both CA-125 response (in recurrent ovarian cancer) and PSA response (in recurrent prostate cancer) have been published [*JNCI* 96:487-488, 2004; *J Clin Oncol* 17, 3461-3467, 1999; *J Clin Oncol* 26:1148-1159, 2008]. In addition, the Gynecologic Cancer Intergroup has developed CA-125 progression criteria which are to be integrated with objective tumor assessment for use in first-line trials in ovarian cancer [*JNCI* 92:1534-1535, 2000].

Cytology, Histology. These techniques can be used to differentiate between partial responses (PR) and complete responses (CR) in rare cases (*e.g.*, residual lesions in tumor types, such as germ cell tumors, where known residual benign tumors can remain).

The cytological confirmation of the neoplastic origin of any effusion that appears or worsens during treatment when the measurable tumor has met criteria for response or stable disease is mandatory to differentiate between response or stable disease (an effusion may be a side effect of the treatment) and progressive disease.

